## 2.2 Secondary objectives

### Secondary endpoints:

#### General :

Overall disease activity measures (BDCAF-Behçet's Disease Current Activity Form)

Reduced need for corticosteroid treatment (reduction of corticosteroid dosage)

Course of other BD-related manifestations

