### **5.5.6 Rescue medication**

A rescue treatment with increased doses of prednisolone or intravenous methyl prednisolone pulses could be used depending on worsening of BD manifestations at the discretion of the investigator.

If no response or worsening of neurologic/vascular manifestations were observed in the first week, rescue treatment decision should be given with the repeated CSF and MRI (neurologic) or CT/Doppler (vascular) analyses.

Following protocol will be used as rescue treatment in patients with worsening symptoms:

For patients with neurologic involvement: 5-10 days of 1000 mg intravenous methyl prednisolone, followed by 1 mg/kg/day prednisolone, if still an insufficient response is observed, 1000 mg intravenous cyclophosphamide

For patients with vascular involvement: 3 days of 1000 mg intravenous methyl prednisolone, followed by 1 mg/kg/day prednisolone, if still an insufficient response is observed, 1000 mg iv cyclophosphamide.

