### **5.5.7 Concomitant treatment**

The investigator should instruct the patient to notify the study site about any new medications he/she takes after the patient was enrolled into the study. All medications, procedures and significant non-drug therapies (including physical therapy and blood transfusions) administered after the patient was enrolled into the study must be recorded.

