### **5.9.4 Steroid Tapering**

Prednisolone dosage should be 20 mg or less at baseline, and it should not be increased during the trial.

At the end of Day 30, complete responders begin to decrease the steroid doses. Tapering target will be 2,5 mg for every 2 weeks. At Day 120, patients expected to use prednisolone no more than 5 mg / day.

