## **8.5 Analysis of secondary variables**

### **8.5.1 Efficacy variables**

Kaplan-Meier estimates will be presented for time to relapse.

Continuous endpoints (steroid tapering, VAS scores, BDCAF scores) will be summarized by mean, standard deviation, median, median, interquartile range, minimum and maximum.

Differences between pre-treatment and post-treatment values will be analysed by the non-parametric Wilcoxon signed rank test at the 0.05 level of significance.

Correlations between the different parameters will be explored by Spearman's rank correlation coefficient.

Categorical variables will be summarized by absolute frequencies and percentages.

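### The steroid-need endpoint has no rule for rescue steroid, so a lower visit dose can be reported as reduced need despite similar or higher total exposure

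*Combined protocol and SAP*

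**What the plan says.** The protocol summary lists need for steroid among its four efficacy assessments. Section 2.2 turns this into "Reduced need for corticosteroid treatment (reduction of corticosteroid dosage". It does not say whether dosage means the current daily dose or a total, at which time it is compared, or what happens after rescue.

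The analysis sections add little. Section 8.5.1 treats steroid tapering as a continuous endpoint and states: "Differences between pre-treatment and post-treatment values will be analysed", by a Wilcoxon signed rank test. Section 3.4 places steroid evaluations at months 3 and 6, and section 8.6 places analyses at Days 30, 90, 180 and 360. Section 8.4.1 lists, among the primary variables, the percentage of patients with appropriate tapering, but does not define appropriate.

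On tapering, section 5.9.4 says: "Prednisolone dosage should be 20 mg or less at baseline, and it should not be increased during the trial". It continues: "At the end of Day 30, complete responders begin to decrease the steroid doses", and "Tapering target will be 2,5 mg for every 2 weeks", with no more than 5 mg/day expected at Day 120.

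On rescue, section 5.5.6 gives "3 days of 1000 mg intravenous methyl prednisolone, followed by 1 mg/kg/day prednisolone" for vascular patients and "5-10 days of 1000 mg intravenous methyl prednisolone, followed by 1 mg/kg/day prednisolone" for neurologic patients. The length of the oral course is not stated.

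On data, the assessment schedule marks a steroid usage assessment at every visit, and section 5.5.7 requires recording of "All medications, procedures and significant non-drug therapies" after enrolment. Section 5.8 names only medication name and reason as fields.

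**The concern.** The most natural reading of sections 2.2, 3.4, 8.5.1 and 8.6 is a comparison of the dose at baseline with the dose on an analysis day. From Day 30 the visits are 30 days apart. A 3- to 10-day pulse can fall wholly between two visits, and the oral course shows only if a visit falls inside it. Nothing in the plan then brings that steroid into the endpoint.

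Rescue is given when disease worsens on canakinumab. If it is left out, the measure of steroid need is most favourable in the patients in whom the drug did least. With 10 patients in an open-label study, one patient is 10 percentage points of the tapering variable, and the choice of how to count a rescued patient could be made after the data are seen.

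**Working it through.** **Inputs from the documents.** Baseline dose 20 mg/day or less, taper of 2.5 mg every 2 weeks from Day 30, and 5 mg/day or less at Day 120 (5.9.4); pulses of 1000 mg for 3 days or for 5-10 days (5.5.6); follow-up to Day 360 (assessment schedule).

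**Assumptions.** The documents give no conversion factor, so mg are counted one for one. The taper stops at 5 mg/day and is held there. The first step is on Day 30 or Day 44, since the text allows both. The oral rescue course is left out of the totals and is assumed to have ended, with the dose back at 5 mg/day.

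**The plan's own figure.** Dose at Day 120 = 20 - 2.5 x steps. First step on Day 44: 6 steps, 20 - 15 = 5 mg/day. First step on Day 30: 7 steps if not stopped at 5 mg, 20 - 17.5 = 2.5 mg/day. Both meet the stated target.

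**Pulse totals.** Vascular: 3 x 1000 = 3,000 mg. Neurologic: 5 x 1000 to 10 x 1000 = 5,000-10,000 mg.

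**Baseline 20 mg/day, 360 days.**
- Constant dose: 20 x 360 = 7,200 mg.
- Taper, first step Day 30: 20 x 30 + 14 x (17.5 + 15 + 12.5 + 10 + 7.5) + 5 x 260 = 600 + 875 + 1,300 = 2,775 mg.
- Taper, first step Day 44: 20 x 44 + 875 + 5 x 246 = 880 + 875 + 1,230 = 2,985 mg.

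**Baseline 10 mg/day, 360 days.**
- Constant dose: 10 x 360 = 3,600 mg.
- Taper, first step Day 30: 10 x 30 + 14 x 7.5 + 5 x 316 = 300 + 105 + 1,580 = 1,985 mg.
- Taper, first step Day 44: 10 x 44 + 105 + 5 x 302 = 440 + 105 + 1,510 = 2,055 mg.

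| Baseline | Constant | Taper alone | Taper + vascular pulse | Taper + neurologic pulse |
|---|---|---|---|---|
| 20 mg/day | 7,200 mg | 2,775-2,985 mg | 5,775-5,985 mg (lower) | 7,775-12,985 mg (higher) |
| 10 mg/day | 3,600 mg | 1,985-2,055 mg | 4,985-5,055 mg (higher) | 6,985-12,055 mg (higher) |

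**Effect on the pre/post difference.** From 20 mg/day, the visit dose gives 5 - 20 = -15 mg/day, a 75% reduction. Average exposure per day minus baseline is:
- neurologic: 7,775/360 - 20 = +1.6 to 12,985/360 - 20 = +16.1 mg/day;
- vascular: 5,775/360 - 20 = -4.0 to 5,985/360 - 20 = -3.4 mg/day.

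From 10 mg/day, the visit dose gives -5 mg/day, while a vascular pulse gives 4,985/360 - 10 = +3.8 to 5,055/360 - 10 = +4.0 mg/day.

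**Sensitivity.**
- If 1 mg of methylprednisolone counts as 1.25 mg (assumed), the 20 mg/day totals become 6,525-6,735 mg (vascular, still lower) and 9,025-15,485 mg (neurologic, higher).
- If the taper goes to 0 with a first step on Day 44, the total before rescue is 880 + 14 x 70 = 1,860 mg. A 5,000 mg pulse then gives 6,860 mg, below 7,200 mg at one for one.
- From 20 mg/day, a vascular pulse exceeds constant dosing once the oral course adds 7,200 - 5,985 = 1,215 mg. At 1 mg/kg/day that is about 14-24 days for an assumed 90-50 kg, ignoring the daily dose that it replaces.
- Daily prednisolone was not subtracted on pulse days. It is at most 10 x 20 = 200 mg and changes no direction in the table.

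**The case against.** A reader might infer three stronger things, and the documents support none of them.

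*That rescue steroid is never counted.* No section excludes it. Steroid usage is assessed at every visit and all medications are recorded. A rescued patient might also be classed as a tapering failure, because 5.9.4 says prednisolone should not be increased and 8.4.1 counts appropriate tapering. But neither section states that link, so the treatment of rescue is undefined rather than excluded.

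*That rescued patients vanish from the summaries.* Section 5.5.10 analyses all data up to discontinuation, section 5.7 schedules a visit 8 weeks after the last dose with the final-visit assessments, and section 8.1 presents all dosed patients.

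*That rescue always reverses the result.* It does not, as the vascular case at 20 mg/day and the taper to 0 show.

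The strongest objection is to the illustration itself. The oral course at 1 mg/kg/day would interrupt the taper. If it came down at the only rate stated, 2.5 mg every 2 weeks (an assumption, since none is given for rescue), falling from 70 to 5 mg takes 65/2.5 = 26 steps, or 52 weeks. From 50 mg it takes 45/2.5 = 18 steps, or 36 weeks. Monthly visits would then show the raised dose. This stands: a visit dose of 5 mg/day after rescue needs a faster return or an early rescue. The case is also narrower because only complete responders are told to taper, and deteriorating patients leave at month 1. A 20 mg/day baseline is itself at the limit that 5.5.8 prohibits. The 10 mg/day row does not depend on that limit.

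Finally, the study is exploratory and unpowered, and failure is also seen in exacerbation counts and time to relapse. That limits the weight of the point but does not define the endpoint.

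**Conclusion.** The gap is real and of moderate importance. The plan equates need with dosage and has no rule for rescue steroid, so a pulse between visits can be missed and a lower dose reported despite similar or higher total exposure.

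In the illustration, a neurologic pulse turns a reported 75% reduction from 20 mg/day into a 360-day total 8% to 80% above constant dosing (7,775/7,200 and 12,985/7,200). A vascular pulse only shrinks the saving at 20 mg/day but exceeds constant dosing at 10 mg/day. These figures rest on one-for-one counting, a return to 5 mg/day and omission of the oral course. The direction for an individual depends on baseline dose, pulse length, final dose and the course after rescue.

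**What to change.** In sections 2.2 and 8.5.1, add cumulative prednisolone-equivalent dose per day of follow-up, from Day 0 to Day 360 or last contact, in all dosed patients, including every rescue pulse and oral rescue course. State the conversion factor. Compare the result with the patient's own Day 0 daily dose.

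With n = 10, one 10,000 mg pulse would dominate a mean, so summarise by median and an individual listing. Report patients on no steroid at Day 0 separately, because they cannot show a reduction. Show the number rescued beside the result, and keep the visit dose as a supportive summary. In 8.4.1, define appropriate tapering and state whether a rescued patient counts as a failure.

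Confirm that the CRF records steroid dose and start and stop dates, since section 5.8 names only medication name and reason. If it does, the cost is wording and a derived variable; if not, CRF fields must be added. The reported steroid saving may become smaller.

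Separately, section 5.5.6, which permits rescue steroid, must be reconciled with sections 5.5.8 (high-dose steroid prohibited), 5.5.9 (prohibited medication requires discontinuation) and 5.9.4 (no increase). Until then, it is unclear whether a rescued patient stays on study treatment.

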#### For NBS:

Time to at least 50% resolution of the MRI lesion as defined above

Assessment of parenchymal lesions by MR spectroscopy, and when possible with functional MRI (f-MRI) and MR-tractography

Preservation of remission within first 12 months

Number of exacerbations within 12 months

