#### For vascular disease:

[figure not shown]
Radiological changes by PET-CT and/or MR imaging

Time to resolution as defined above

Preservation of remission within 12 months

Number of recurrent exacerbations within 12 months

PK, PD evaluations in serum and CSF

[figure not shown]

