### **5.5.8 Prohibited Treatment**

The following treatments are NOT allowed prior to baseline (time intervals prior to baseline are detailed below) AND during the entire study:

- Etanercept in the 4 weeks prior to the baseline visit (Day 0) and thereafter
- Riloncept in the 3 weeks prior to the baseline visit (Day 0) and thereafter
- Adalimumab in the 8 weeks prior to the baseline visit (Day 0) and thereafter
- Infliximab in the 12 weeks prior to the baseline visit (Day 0) and thereafter
- Rituximab in the 26 weeks prior to the baseline visit (Day 0) and thereafter
- Any other investigational biologics in the 8 weeks prior to the baseline visit (Day 0) and thereafter (with the exception of anakinra therapy –see below)
- Kineret (anakinra therapy) 3 days prior to the baseline visit (Day 0) and thereafter
- Leflunomide in the 4 weeks prior to the baseline visit (Day 0) and thereafter. After the completion of leflunomide treatment a cholestiramine in dose 8 g 3 times per day for 14 days is recommended.
- Thalidomide in the 2 weeks prior to the baseline visit (Day 0) and thereafter
- Cyclosporine in the 2 weeks prior to the baseline visit (Day 0) and thereafter
- i.v. immunoglobulin (i.v. Ig) in the 8 weeks prior to the baseline visit (Day 0) and thereafter
- 6-Mercaptopurine, cyclophosphamide, or chlorambucil in the 12 weeks prior to the baseline visit (Day 0) and thereafter
- Dapsone, in the 3 weeks prior to the baseline visit (Day 0) and thereafter
- Corticosteroids  $\geq 20\text{mg/day}$  or  $>0.4 \text{ mg/kg}$ , whichever applies, in the 1 week prior to the baseline visit (Day 0) and thereafter
- Live vaccinations within 3 months prior to the start of the trial, during the trial, and up to 3 months following the last dose.
- Use of other investigational non-biological drugs at the time of enrollment, within 30 days or 5 half-lives of enrolment, whichever is longer.
  - Intravenous methyl prednisolone pulse treatment within the last month

The investigator should instruct the patient to notify the study site about any new medications he/she takes after the start of the study drug. All medications and significant non-drug therapies (including physical therapy and blood transfusions) administered after the patient starts treatment with study drug must be listed on the Concomitant medications/Significant non-drug therapies after start of study drug.

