### **5.5.9 Discontinuation of study treatment**

Study drug must be discontinued for a given patient if the investigator determines that continuing it would result in a significant safety risk for that patient. The following circumstances require study drug discontinuation:

- Emergence of the following adverse events:
  - in the case of any severe or serious adverse event that is not compatible with administration of study medication, including adverse events that require treatment with an unacceptable co-medication,
  - in the case of onset of malignancy,
  - in the case of an uncontrolled life-threatening infection.
- Pregnancy
- Use of the prohibited concomitant medications
- Withdrawal of informed consent

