## 5.7 Patient demographics/other baseline characteristics

Patient demographic and baseline characteristic data to be collected on all patients include: date of birth, age, sex, ethnicity, patient referral source, relevant medical history/current medical condition present before signing informed consent. Where possible, diagnoses will be recorded, not symptoms.

Subjects should be seen for all post-baseline visits on the designated day with the allowance of a  $\pm 7$  day window for all visits. Subjects who discontinue study drug before completing the study, and those who prematurely withdraw from the study for any reason, should be scheduled for a visit 8 weeks ( $\pm 1$  week) after their last infusion /injection, at which time all of the assessments listed for the final visit will be performed.

Subjects who discontinue study drug also should return for a last assessment. If they refuse to return for this or are unable to do so, every effort should be made to contact them or a knowledgeable informant by telephone to determine the reason for discontinuation. At a minimum, they will be contacted for safety evaluations during the 30 days following the last dose of study drug, including final contact at the 30-day point. Documentation of attempts to contact the patient should be recorded in the patient record.

Information that will be collected on subjects who are screened but not enrolled includes patient demographics (age, gender, and ethnicity) and primary reason for not continuing.

If a patient discontinues before entering Visit 1, only the demographic information and Screening Log entry with the primary reason for discontinuation should be completed on the CRF. It is not necessary to complete all the required evaluations at the time of discontinuation unless medically indicated.

At screening visit information on age, sex, will be collected. Relevant medical history/current medical conditions, family medical history, will be recorded on the respective CRF page. The following should be recorded on the respective CRF page.

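### The 12-month exacerbation counts make no allowance for observed time, and on a literal reading a rescued exacerbation ends most later observation, so the counts would understate the yearly burden

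*Combined protocol and SAP*

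**What the plan says.** Section 2.2 lists, as secondary endpoints, "Number of exacerbations within 12 months" (neurologic) and "Number of recurrent exacerbations within 12 months" (vascular). Section 8.5.1 plans a Kaplan-Meier estimate of time to relapse. It gives no method for the counts beyond generic descriptive summaries: no rate, no person-time, and no rule for patients seen for less than 12 months.

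Four other sections decide how long a patient is observed after an exacerbation:

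- **5.5.6** allows rescue, which "could be used depending on worsening of BD manifestations at the discretion of the investigator". For neurologic patients it consists of "5-10 days of 1000 mg intravenous methyl prednisolone, followed by 1 mg/kg/day prednisolone", with cyclophosphamide if the response is insufficient. The vascular scheme has a shorter pulse and the same later steps.
- **5.5.8** opens with "The following treatments are NOT allowed prior to baseline (time intervals prior to baseline are detailed below) AND during the entire study". Its list includes cyclophosphamide and corticosteroids at or above a stated daily threshold, both also after baseline.
- **5.5.9** lists "Use of the prohibited concomitant medications" among the circumstances that require study drug to be stopped. Rescue is not exempted.
- **5.7** says that patients who stop study drug early, and "those who prematurely withdraw from the study for any reason, should be scheduled for a visit 8 weeks" (±1 week) after the last dose, have the final-visit assessments then. No later visit is scheduled for them.

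Sections 3.1 and 5.5.5 also remove non-responding or deteriorating patients at month 1.

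**The concern.** The event being counted can itself close the period in which further events could be counted. A patient who relapses early and is rescued contributes a short observed period but is tabulated under a 12-month label, next to patients seen for the full year. The more active the disease, the more of the year goes unseen.

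The counts are the only listed endpoints that could show repeated relapse. If they collapse towards a yes/no, frequent relapsers are hidden and the error favours the drug. With a single arm, the absolute figure is all a reader has; no control group shares the same truncation.

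**Working it through.** The plan states no exacerbation rate, rescue share or expected count, so there is no figure of its own to reproduce. All rates below are assumptions.

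**One patient.** An exacerbation is rescued on Day 100. The last dose was on Day 90, so the final visit falls on Day 90 + 56 = Day 146 (139 to 153 with the window). Observed share: 146/360 = 41%. The table shows one exacerbation within 12 months, the same as for a patient with one exacerbation seen on all 360 days.

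**Expected counts, Day 30 to Day 360.** Take T = 330/365.25 = 0.9035 years, a constant rate λ per patient-year, and every exacerbation rescued with a prohibited drug.

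- True expected count: λT.
- Observed count if observation ends at the first event: 1 − exp(−λT).
- Observed count with the 8-week visit: λ × mean observed time. Doses are about 30 days apart, so 56 − U days remain after the event, with U uniform on 0 to 30 (26 to 56 days), cut off at Day 360. This was simulated.

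| λ per year | True λT | Ends at first event | Shortfall | With 8-week visit | Shortfall | Share of window observed |
|---|---|---|---|---|---|---|
| 0.5 | 0.45 | 0.36 | 20% | 0.38 | 15% | 85% |
| 1 | 0.90 | 0.59 | 34% | 0.66 | 27% | 73% |
| 2 | 1.81 | 0.84 | 54% | 1.02 | 44% | 56% |

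**Second check, Day 0 to Day 360, doses every 30 days, 8-week visit captured.** Raw count as a percentage of the true count:

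| λ per year | All rescued | Half rescued |
|---|---|---|
| 0.25 | 91% | 96% |
| 0.5 | 83% | 91% |
| 1 | 70% | 83% |
| 2 | 53% | 70% |

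With all rescued, the chance of recording two or more exacerbations falls from 0.26 to 0.07 at 1 per year, and from 0.59 to 0.17 at 2 per year. If 20% of patients also leave at month 1 (assumed, with observation ending at Day 30), the 70% at 1 per year becomes 57%.

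**Does person-time repair it?** If all patients share one constant rate, events divided by observed time returns that rate within simulation error (1.00 for 1, 1.99 for 2). If rates differ it does not quite. Take half the patients at 0.25 and half at 2 per year (true mean 1.125), all rescued, Day 30 to Day 360:

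- Ending at the first event, the pooled rate is 0.85 (25% low) and the raw count is 0.52 against a true 1.02 (49% low).
- With the 8-week visit, the pooled rate is 0.92 (19% low) and the raw count is 0.61 against 1.02 (40% low).

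The pooled rate still understates, but by about half as much as the raw count.

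**The case against.** The strongest reply is that the truncation rests on one side of a contradiction. Section 5.5.6 offers rescue within the protocol and never says that it ends study drug or follow-up. The glossary separates stopping treatment from withdrawing. A 12-month count of recurrences also fits best with patients remaining under observation. This stands: the cap is conditional. What it does not remove is the literal route through 5.5.8, 5.5.9 and 5.7, or the absence of any denominator for patients who leave early for other reasons, including the month-1 exits.

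A reader might infer that the plan treats unseen time as free of exacerbations. The documents do not say so. No section imputes zero events, and 5.5.10 says that data up to discontinuation will be analysed. The plan is silent, and the risk lies in how a count with a 12-month label will be read.

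The Kaplan-Meier estimate in 8.5.1 can handle censored follow-up, and preservation of remission is a separate endpoint. So durability does not depend on this count alone. Neither of them measures repeated exacerbations.

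Some worsening could be picked up outside visits as an adverse event (6.1), or as a serious event up to 30 days after the last dose (6.2.2). That period ends before the 8-week visit, so it adds little to the later, unseen part of the year.

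Finally, rescue is discretionary, so the all-rescued figures are a worst case. At 0.5 per year with the 8-week visit, the loss is 0.45 − 0.38 = 0.07 per patient, under one event in 10 patients.

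**Conclusion.** The concern holds in conditional form. The two counts lack any allowance for observed time. On the literal text, a rescued exacerbation ends most later observation, so the count is held near one for rescued patients and understates the 12-month burden. It is not a strict cap at one: a second event can fall before the 8-week visit, and exacerbations managed without a prohibited drug do not shorten follow-up.

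The shortfall is about 15%, 27% and 44% at assumed constant rates of 0.5, 1 and 2 per year with every exacerbation rescued. It is less if rescue is partial, and the rescue-driven part is nil if rescued patients stay under observation. The tempting stronger statement, that the reported counts will be wrong by these amounts, is not supported: neither the rate nor the rescue share is in the documents, and the sections on rescue and stopping conflict.

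For a secondary endpoint in an exploratory study of about 10 patients, this is a cheap improvement, not a threat to the primary result.

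**What to change.** - In 2.2 and 8.5.1, report exacerbations per patient-year: total exacerbations divided by total observed time, from Day 0 to the last attack assessment, in all dosed patients. Give a 95% Poisson interval, labelled approximate because exposure can end at an event.
- List each patient's count beside the days observed, and read the rate alongside the Kaplan-Meier estimate of time to relapse.
- State that the pooled rate removes the bias fully only if patients share a constant rate. With differing rates it still understates, though less than the raw count.
- Reconcile 5.5.6, 5.5.8, 5.5.9 and 5.7 so that they say one thing on whether observation continues after a rescued exacerbation. Which clinical rule applies is for the sponsor and investigators to settle.

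The cost is some wording and one table; visit dates and attack assessments are already recorded. The downside is a wide interval with about 10 patients and, probably, a less favourable figure.
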